Study Design: Biomedical

1. Will controls be used?

Yes

► IF YES, explain the kind of controls to be used.

The control group will receive placebo on the same schedule that the investigational agent is administered, namely every 8 hours for 72 hours. The placebo will be prepared by our investigational pharmacy and dispensed by the same.

2. What is the study design?

Randomized, Double-Blind Placebo-Controlled Trial

3. Does the study involve a placebo?

Yes

► IF YES, provide a justification for the use of a placebo

Placebo is justified to provide for blinding of the nursing staff and study investigators who might otherwise confound study results by weaning vasopressors more or less aggressively than usual practice.

Human Participants

Ages: 18-89 years of age

Sex: BOTH

Race: ANY

Subjects- see below

1. Provide target # of subjects (at all sites) needed to complete protocol.

To estimate the sample size, we used the UVA Clinical data repository (CDR) to identify 960 patients who would have met our study enrollment criteria (patients receiving IV vasopressors for >3 hours, with a diagnosis of sepsis, without cirrhosis, and not receiving midodrine). We then extracted their duration of vasopressors and the total norepinephrine equivalent doses at 24 hours. We performed repeated simulation of bootstrapped samples to estimate power from these populations with varying sample and effect sizes. Based on these estimates, we believe that a final sample size of 50 per group will provide 80% power to detect a 12-hour difference in duration of IV vasopressors based on a 2-arm study design (placebo vs midodrine). These calculations compare favorably with those obtained assuming a normal distribution, based on a mean IV vasopressor duration of 54.9 hours (SD 28.4 h) in patients with septic shock as published in a recent trial⁹, which calculations would require randomization of 49 patients to each group to detect an effect of 18 hours difference in IV vasopressor duration at a power of 80% and an alpha value of 0.05. However, because our calculations are based on internal data (and so should reflect our practices of vasopressor weaning) and because the distribution of IV vasopressor duration is non-normal, we believe that sample size calculation based upon our CDR analysis is more accurate.

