To address questions regarding dosing both in terms of efficacy and safety, we will plan for an “early phase” of the study, which will essentially serve as a nested dose-response study. In this “early phase” we will randomize the first 45 subjects to one of 3 study arms (placebo, midodrine 10 mg thrice daily or midodrine 20 mg thrice daily). For the interim analysis of this “early phase”, a final sample size of 15 patients per group will provide 80% power to detect a 5 mcg/min decrease in norepinephrine equivalents at 24 hours.

Together with our “early phase” nested study and anticipating a 25% mortality in patients with septic shock we would need to enroll 115 patients to reach statistical significance. Enrolling 115 patients would allow randomization of 50 patients to placebo and 50 patients to the midodrine dose continued following the “early phase” (either 10 or 20 mg depending on the results of our interim analysis at which time we will evaluate both the safety and efficacy of both dosing strategies and continue the lowest dose that is both safe and efficacious). The additional 15 subjects would be required for the early dose-response portion of the study.

In brief:

115 total subjects: 50 placebo, 50 midodrine (either 10mg or 20mg); 15 additional subjects for the “early phase” portion of the study

2. Describe expected rate of screen failure/ dropouts/withdrawals from all sites.

Average mortality in septic shock is anticipated to be around 25-30%. Screen failure is anticipated to be around 20%, mostly due to patients with decompensated cirrhosis. This is based on our MICU septic shock database.

3. How many subjects will be enrolled at all sites?

149

4. How many subjects will sign a consent form under this UVa protocol?

149

Inclusion/Exclusion Criteria

1. List the criteria for inclusion

- Patients aged \geq 18-89 years old
- Admitted to UVA medical ICU with diagnosis of septic shock.
- Patients requiring at least 5 mcg/min norepinephrine infusion (or equivalent) for blood pressure support for at least 3 hours
- Patients with enteral access established within 12 hours of admission (either able to swallow, or feeding tube in place)

2. List the criteria for exclusion

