- Midodrine HCl has been used in patients concomitantly treated with salt-retaining steroid therapy (i.e., fludrocortisone acetate), with or without salt supplementation. The potential for supine hypertension exists in these patients and may be minimized by either reducing the dose of fludrocortisone acetate or decreasing the salt intake prior to initiation of treatment with Midodrine HCl.
- Alpha-adrenergic blocking agents, such as prazosin, terazosin, and doxazosin, can antagonize the effects of Midodrine HCl.

Patients will be continuously monitored in ICU and the goal of the study is to raise blood pressure.

Statistical Considerations

1. Is stratification/randomization involved?

YES

► IF YES, describe the stratification/ randomization scheme.

After enrollment, patients will initially be randomized employing a block of 9 randomization scheme generated by the study investigators. Allocation will be performed manually; there will be 5 envelopes, each envelop for a sequence of 9 patients. Each envelope will contain 3 cards for the placebo group and 3 cards for the midodrine 10 mg TID treatment group and 3 cards for the midodrine 20 mg TID treatment group. Cards will be pulled out of the envelope to randomize the patients. Once 9 patients are randomized the next envelop will be opened.

Following interim analysis of the first 45 patients, one of the treatment groups will be dropped with preference given to dropping the midodrine 20 mg TID group should interim analysis demonstrate similar, significant effect sizes in both treatment groups. Additionally, the safety profile of both dosing strategies will be considered prior to continuing the experimental arm of the study.

Subsequently, the remaining 104 patients will be randomized employing a block of 8 randomization scheme generated by the study investigators. Allocation will be performed manually; there will be 13 envelopes, each envelop for a sequence of 8 patients. Each envelope will contain 4 cards for the placebo group and 4 cards for the continuing midodrine group (either 10 mg TID or 20 mg TID). Cards will be pulled out of the envelope

to randomize the patients. Once 8 patients are randomized the next envelop will be opened.

► IF YES, who will generate the randomization scheme?

Sponsor
 UVa Statistician. Answer/Response:
 UVa Investigational Drug Service (IDS)
 Other: Answer/Response: Investigators
UVa Investigational Drug Service (IDS)

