2. What are the statistical considerations for the protocol?

We will compare placebo group versus the midodrine intervention group for all primary analyses and use the Mann-Whitney U test to assess the primary outcome, which is assumed to be non-parametric.

3. Provide a justification for the sample size used in this protocol.

To estimate the sample size, we used the UVA Clinical data repository (CDR) to identify 960 patients who would have met our study enrollment criteria (patients receiving IV vasopressors for >3 hours, with a diagnosis of sepsis, without cirrhosis, and not receiving midodrine). We then extracted their duration of vasopressors and the total norepinephrine equivalent doses at 24 hours. We performed repeated simulation of bootstrapped samples to estimate power from these populations with varying sample and effect sizes. Based on these estimates, we believe that a final sample size of 50 per group will provide 80% power to detect a 12-hour difference in duration of IV vasopressors (our primary end point) based on a 2-arm study design (placebo vs midodrine). These calculations compare favorably with those obtained assuming a normal distribution, based on a mean IV vasopressor duration of 54.9 hours (SD 28.4 h) in patients with septic shock as published in a recent trial⁹, which calculations would require randomization of 49 patients to each group to detect an effect of 18 hours difference in IV vasopressor duration at a power of 80% and an alpha value of 0.05. However, because our calculations are based on internal data (and so should reflect our practices of vasopressor weaning) and because the distribution of IV vasopressor duration is non-normal, we believe that sample size calculation based upon our CDR analysis is more accurate.

To address questions regarding dosing both in terms of efficacy and safety, we will plan for an “early phase” of the study, which will essentially serve as a nested dose-response study. In this “early phase” we will randomize the first 45 subjects to one of 3 study arms (placebo, midodrine 10 mg thrice daily or midodrine 20 mg thrice daily). For the interim analysis of this “early phase”, a final sample size of 15 patients per group will provide 80% power to detect a 5 mcg/min decrease in norepinephrine equivalents at 24 hours.

Together with our “early phase” nested study and anticipating a 25% mortality in patients with septic shock would need to enroll 149 patients to reach statistical significance.

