Secondary outcomes will include ICU and hospital length of stay as well as central venous catheter dwell time. Because IV vasopressor duration cannot be assumed to have a normal distribution, we intend to analyze our primary outcome using the Mann-Whitney U test.

4. What is your plan for primary variable analysis?

Dose of IV vasopressor(s) at 24 hours and hours requiring IV vasopressor therapy will be the primary outcomes of interest for the “early phase” and complete study, respectively. Because IV vasopressor duration and dose cannot be assumed to have normal distributions, we intend to analyze our primary outcome using the Mann-Whitney U test.

5. What is your plan for secondary variable analysis?

1. Central venous catheter free days
2. Hospital length of stay
3. Intravenous Vasopressor free days
4. 28-day mortality
5. ICU mortality
6. Need for re-initiation of vasopressor therapy after discontinuation for >2 hours

We will employ the Chi square test for binary outcomes. Furthermore, we will use regression analyses with appropriate interaction terms.

6. Have you been working with a statistician in designing this protocol?

No

IF YES, what is their name?

Answer/Response:

N/A

7. Will data from multiple sites be combined during analysis?

No

INSTRUCTIONS: IF YES, answer the following questions

7(a). Does the study involve randomization?

Answer/Response:

IF YES, will randomization be done at each site or among sites?

Answer/Response:

7(b). Has the sample size calculation considered the variation among sites?

Answer/Response:

7(c). When combining the data from multiple sites to assess the study results, is the effect of the treatment to be tested (or the association to be tested) assumed to be the same across sites or vary among sites? What is the modelling strategy?

Answer/Response:

7(d). Is there a common protocol used in all sites?

Answer/Response:

IF NO, how will differences among sites, such as those related to the implementation, inclusion criteria, patient characteristics, or other sites characteristics, be considered to assess the study results?

Answer/Response:

Study Procedures-Biomedical Research

1. What will be done in this protocol?

Screening:

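### The normal-theory check offered beside the 12-hour power claim is made at 18 hours, its 49 per group does not follow from its stated inputs, and the 115 said to anticipate mortality contains no allowance for it

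*Combined protocol and SAP*

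**What the plan says.** The same justification is printed twice, in Human Participants item 1 and in Statistical Considerations item 3. It makes four statements about the primary outcome.

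- The main calculation resamples 960 repository patients: "We performed repeated simulation of bootstrapped samples to estimate power from these populations with varying sample and effect sizes". Its result is that a "final sample size of 50 per group will provide 80% power to detect a 12-hour difference in duration of IV vasopressors".
- A second calculation is set beside it: "These calculations compare favorably with those obtained assuming a normal distribution, based on a mean IV vasopressor duration of 54.9 hours (SD 28.4 h"). That second calculation "would require randomization of 49 patients to each group to detect an effect of 18 hours difference in IV vasopressor duration", at 80% power and an alpha of 0.05.
- The authors prefer the first, because it uses internal data and the outcome is not normal: "we believe that sample size calculation based upon our CDR analysis is more accurate". Statistical Considerations item 4 repeats that "IV vasopressor duration and dose cannot be assumed to have normal distributions" and names the Mann-Whitney U test.
- On totals, Human Participants item 1 says that 115 patients are needed with 25% mortality anticipated, and that "Enrolling 115 patients would allow randomization of 50 patients to placebo and 50 patients to the midodrine dose" carried forward, plus 15 for the early phase. Items 3 and 4 of the same section give 149, as does Statistical Considerations item 3. Item 1 of Statistical Considerations says that after the first 45, "the remaining 104 patients will be randomized employing a block of 8 randomization scheme", and Study Procedures item 1 uses the same 45 and 104.

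**The concern.** A reader sees 50 per group from one method and 49 per group from another and takes the two as agreeing. They answer different questions: one is for 12 h and the other for 18 h. Required sample size varies with the inverse square of the difference, so nearly equal numbers at these two effects point to disagreement unless the two methods use quite different variability or distributional shape.

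The normal-theory calculation is also the only one whose inputs are printed. If its stated result does not follow from those inputs, the one part of the justification that can be checked fails the check. The two enrolment totals add a further doubt, because the justification does not say consistently whether 50 per arm is the number randomised or the number left after losses.

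**Working it through.** **Inputs.** From the plan: SD 28.4 h, alpha 0.05, power 80%, two equal groups, differences of 18 h and 12 h. Sidedness is not stated, so two-sided is assumed. No loss allowance is stated for the 49, so none is applied.

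**Formula.** n per group = 2 × [(1.960 + 0.842) × SD / d]².

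**Step 1: the plan's own figure, 18 h.**
- n = 2 × (2.802 × 28.4 / 18)² = 39.08, so 40 per group. The t-test version gives 40.06, so 41.
- The plan prints 49. With 49 per group, power at 18 h would be 87–88%, not 80%.
- Variants that keep to a normal-theory comparison and still miss: one-sided, 31; 85% power, 45; 90% power, 53.
- Variants that reach 49 each need something the sentence does not state: 39.08 × 1.25 = 48.8; 39.08 / 0.80 = 48.8; a two-sided level of 0.025 with a t-test, 48.6; a three-arm ANOVA with one mean midway, 48.98.

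**Step 2: the same calculation at 12 h.**
- n = 2 × (2.802 × 28.4 / 12)² = 87.9, so 88 per group. The t-test version gives 88.9, so 89.
- The ratio to the 18 h result is (18/12)² = 2.25, and 39.08 × 2.25 = 87.9.
- A one-sided test would still need 70 per group.

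**Step 3: what 50 per group gives under normality.**
- Standard error = 28.4 × √(2/50) = 5.68 h. At 12 h, 12 / 5.68 − 1.960 = 0.153, so power is 56%; the t-test gives 55%.
- Difference detectable with 80% power: 2.802 × 5.68 = 15.9 h (16.1 h by t-test).
- For 50 per group to give 80% power at 12 h, the SD would have to be 12 / (2.802 × √(2/50)) = 21.4 h.

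**Step 4: the planned Mann-Whitney test on skewed data.** These simulations use the external mean (54.9 h) and SD (28.4 h), 12 h and 50 per group. The shapes are assumptions, not the repository's distribution.

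| Assumed shape | 12 h as a mean difference | 12 h as a median difference (proportional effect) |
|---|---|---|
| Normal, shift | 53% | – |
| Gamma | 61–62% | about 70% |
| Lognormal | 69–72% | 80% |

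So 80% is reachable under some readings and not under others.

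**Step 5: the totals.**
- Human Participants item 1: 50 + 50 + 15 = 115. Nothing is left for the 25% mortality that the sentence says it anticipates.
- Elsewhere: 45 + 104 = 149. Each continuing arm gets 15 + 104/2 = 67, and 67 + 67 + 15 = 149. After 25% loss, 67 × 0.75 = 50.25, or about 50 per arm.

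**The case against.** The strongest reply is that the sample size does not depend on the normal-theory check. The 50 per group comes from the bootstrap, and the plan itself calls the other calculation less accurate. Both effect sizes are printed openly, and the comparison can be read as saying that the bootstrap comes out better (about the same n for a smaller effect), not that the two agree. On that reading no corroboration is claimed. This stands in part: the check is a companion to the claim, not its foundation. But agreement is at least as natural a reading, and a comparison at unequal effects tells the reader little on either.

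A second reply is that the 49 may already include an allowance for losses. It is worded as a number to be randomised, 25% mortality appears nearby, and × 1.25 gives 48.8. That is plausible, and it is why the figure is best called not reproducible from its stated inputs. The discrepancy is also conservative, since 40–41 would suffice for 18 h. The step is nevertheless undisclosed, and other unstated steps fit equally well.

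A reader might infer more: that 50 per group is too few, or that the bootstrap's 80% is wrong. The documents do not support that. The repository SD and shape are not printed, an SD near 21.4 h would give 80% even under normality, and the Mann-Whitney test can gain power on skewed data. Nor do they support the inference that only 115 will be randomised, since the randomisation scheme is built for 149. How 149 was derived is not stated: 100/0.75 rounded up plus 15 fits, but 115 × 1.30 = 149.5 is also close.

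**Conclusion.** The point holds as a fault in the printed justification, in three parts.

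1. The comparison sets a 12 h claim beside an 18 h calculation. Put at 12 h with the external SD, the check gives 88–89 per group, against the 50 planned, so it does not support the claim.
2. The 49 for 18 h does not follow from its stated inputs, which give 40–41. This is the lesser part and errs on the safe side.
3. The total of 115 is described as anticipating 25% mortality when its components leave no room for it, and it conflicts with the 149 used in the rest of the document.

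The first two rest on a two-sided 5% level, the printed SD of 28.4 h and no loss allowance. The third is simple addition. Whether the bootstrap's 80% is right cannot be settled from the documents. It is worth correcting before the justification is relied on, but nothing here shows that the design itself must change.

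**What to change.** Make the changes in both places where the paragraph appears.

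- Delete the statement that the two calculations compare favourably, or restate the check at 12 h: 88–89 per group, and about 55% power with 50 per group, labelled as assuming normality and the external study's SD.
- Replace 49 with 40–41 for 18 h, or state the allowance that the 49 contains.
- Correct Human Participants item 1 so that 115 is not described as including mortality, and so that it agrees with 149. Say which figure counts patients randomised and which counts those left after losses.

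A useful clarification, though not part of the error, is to report the bootstrap's inputs: the cohort's mean, SD and shape, how the effect was imposed, and whether 12 h is a mean or a median difference. It would also help to say whether the entry criterion of at least 5 mcg/min norepinephrine was applied to the 960 patients, since the bracketed description of that cohort does not mention it.

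The cost is a few restated figures. The corrections themselves call for no extra patients. The downside is that the supporting calculation will look less favourable than it does now.

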A growing body of literature comprising largely retrospective data seems to support the safety and efficacy of midodrine in the intensive care unit for decreasing IV vasopressor use³⁻⁵. In the largest retrospective case series to date, Rizvi et al. report that in 663 patients receiving IV vasopressors (in both surgical and medical ICU settings), 48% were liberated from IV vasopressor support within 24 hours of midodrine initiation. Regarding its efficacy in septic shock, Whitson et al. compared a retrospective cohort of patients in the “recovery phase” of septic shock receiving IV vasopressors and midodrine with a comparator cohort of patients receiving only IV vasopressors for the same indication. When compared with the IV vasopressor-only group, a statistically significant decrease in IV vasopressor duration approaching 24 hours was observed in the group receiving midodrine. Additionally, a decrease in ICU-LOS of nearly 2 days was

reported in the group receiving IV vasopressors and midodrine when compared with IV vasopressor-only group⁵. Finally, in a small but prospectively-designed study of 20 patients in a surgical ICU setting receiving a IV vasopressors at a mean phenylephrine equivalent rate of 41 mcg/min, the authors reported a significant acceleration in the decline rate of IV vasopressors⁶.

Importantly, complications attributable to midodrine in the above studies were minor and predominantly consisted of asymptomatic bradycardia, an expected effect of the drug. It is noteworthy that an emerging body of evidence suggests that heart rate control and relative bradycardia are associated with improved outcomes in patients with septic shock^{7,8}. Other adverse events reported have included ischemic bowel in 2 patients (0.18% of the study population), however, these events were not believed to be directly attributable to midodrine, and midodrine was only discontinued in one of these 2 patients³.

On the basis of the described, pre-existing evidence, we hypothesize that administration of midodrine in the early phase of septic shock in patients with adequate enteral access will result in a significant decrease in time to IV vasopressor liberation (increase in vasopressor-free days), secondarily resulting in decreased CVC dwell times and ICU LOS. We aim to perform a randomized, double-blind, placebo-controlled trial to investigate the efficacy of midodrine in decreasing time to IV vasopressor liberation in patients with septic shock.

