7. GCS
8. APACHE IV scores
9. Blood gas data
10. Mortality data (30- and 90-day)
11. Culture data

12. Diagnosis data pulled from provider notes
13. MAR data including concomitant corticosteroid use and antibiotics
14. Imaging data, including CXRs and CTs
15. Vital sign data including temperature, heart rates, blood pressures for the duration of the admission

The standard current ICU level care will be provided to both study groups. Invasive blood pressure measurement, laboratory studies, and imaging studies will be done according to standard practices in septic shock for all groups in the trial.

Intravenous vasopressor will be weaned in both groups as tolerated for MAP goal of > 65 mmHg by the bedside nursing staff according to usual practice (no protocolized algorithm for vasopressor weaning exists, vasopressors are weaned, as long as targeted MAPs are maintained, according to nursing judgment).

Subjects admitted to the ICU with a diagnosis of sepsis and in shock as defined, for study purposes, as requiring any IV vasopressor of at least 5 mcg/min norepinephrine infusion (or equivalent) for at least 3 hours AND with adequate enteral access (oral, orogastric, nasogastric or pre-existing PEG) will be randomized to either midodrine 10 or 20 mg every 8 hours for 72 hours or placebo, to investigate the efficacy of midodrine in decreasing time to IV vasopressor liberation in patients with septic shock. Data collection will continue until hospital discharge.

A dose of up to 20 mg TID is chosen as it was the modal dose in a recent prospective study and is the upper end of dosing with predictable hemodynamic response in another study. The retrospective studies previously referenced reported varying doses up to 40 mg TID.

The standard current ICU level care will be provided to both study groups. Invasive blood pressure measurement, laboratory studies, and imaging studies will be done according to standard practices in septic shock for both arms of trial. Intravenous vasopressor will be weaned in both groups as tolerated for MAP goal of > 65 mmHg by the bedside nursing staff.

2. If this protocol involves study treatment, explain how a subject will be transitioned from study treatment when they have completed their participation in the study.

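### The final primary outcome, raw hours on IV vasopressors, has no rule for patients who die before liberation and no stated analysis set, so taken literally an early death on vasopressors counts as a good result

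*Combined protocol and SAP*

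**What the plan says.** Statistical Considerations, item 4, sets the primary outcomes: "Dose of IV vasopressor(s) at 24 hours and hours requiring IV vasopressor therapy will be the primary outcomes of interest". The first belongs to the early phase and the second to the complete study. Both are to be compared by the Mann-Whitney U test. On who is compared, item 2 says only "We will compare placebo group versus the midodrine intervention group for all primary analyses".

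The aim is given in Study Procedures, item 1, as "to investigate the efficacy of midodrine in decreasing time to IV vasopressor liberation in patients with septic shock". The hypothesis in the Background treats this as equivalent to more vasopressor-free days: "decrease in time to IV vasopressor liberation (increase in vasopressor-free days".

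Human Participants, item 2, states: "Average mortality in septic shock is anticipated to be around 25-30" percent. No time window is attached. Mortality enters the planning only through enrolment (Statistical Considerations, item 3): "anticipating a 25% mortality in patients with septic shock would need to enroll 149 patients to reach statistical significance". It appears in the analysis only as separate secondary outcomes (28-day and ICU mortality). Vasopressor-free days is also secondary, with no window and no value for deaths.

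Nowhere is there a worst rank, a censoring rule, a competing-risk method or an exclusion for deaths, and no analysis population is named. Non-compliance is defined, but nothing in the analysis depends on it.

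**The concern.** Hours on IV vasopressors end either because the patient no longer needs them or because the patient dies. A rank test on raw hours cannot tell these apart. A patient who dies on vasopressors at 20 h was never liberated and gained no time alive and off vasopressors, yet ranks ahead of a survivor weaned at 50 h. For such patients the outcome runs opposite to the aim.

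The alternative suggested by the enrolment arithmetic is to drop the deaths. That compares subsets defined by an event after randomisation, which can differ between arms in ways that randomisation does not protect against.

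Because the plan chooses neither, the choice could be made after the data are seen. At stake are the direction of the final result, if deaths are more frequent or earlier in one arm, and its significance, even when deaths are balanced.

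**Working it through.** **1. The plan's enrolment figure.** Inputs: 50 per group and 25% mortality (Statistical Considerations, item 3), and 15 patients in the dose arm that is dropped (Human Participants, item 1).

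- 50 / 0.75 = 66.7, rounded up to 67; 2 x 67 + 15 = 149. This reproduces the stated total exactly.
- The envelopes agree: 45 / 3 = 15 and 104 / 2 = 52, so 15 + 52 = 67 in placebo and 67 in the continuing arm.
- Expected survivors per arm: 67 x 0.75 = 50.25 at 25% mortality; 67 x 0.70 = 46.9 at 30%.
- Expected deaths per arm: 67 x 0.25 = 16.75; 67 x 0.30 = 20.1.

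The 149 is therefore the number needed to leave 50 survivors per arm. That implies deaths are removed, but no analysis rule says so.

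**2. Simulation set-up.** From the documents: 67 per arm, and a mean of 54.9 h with SD 28.4 h. Assumed, not in the documents:

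- lognormal hours: sigma = sqrt(ln(1 + (28.4/54.9)^2)) = 0.487, median 54.9 / exp(0.487^2 / 2) = 48.8 h;
- time to death on vasopressors lognormal with the same sigma and a median of 27 h (40 h as an alternative);
- the share of deaths that precede liberation: a quarter, half or all;
- any difference in mortality or death timing between arms;
- a two-sided 5% test, so 2.5% in each direction.

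The test is a tie-corrected Mann-Whitney, with 20,000 trials per scenario.

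**3. No effect on weaning: how often midodrine is significantly favoured.** The last three columns are the share of deaths before liberation.

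| Scoring and scenario | Quarter | Half | All |
|---|---|---|---|
| Raw hours, 40% vs 25% mortality, 27 h median to death | 4.1% | 7.1% | 15.2% |
| Same, 40 h median | 3.2% | 3.4% | 5.5% |
| Raw hours, 35% vs 25%, 27 h | 3.4% | 5.3% | 8.6% |
| Same, 40 h | 2.7% | 3.1% | 4.2% |
| Raw hours, equal 25%, median to death 24 h (midodrine) vs 30 h | 3.1% | 4.3% | 6.9% |
| Worst rank, 40% vs 25%, 27 h | 1.1% | 0.4% | 0.0% |

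With equal mortality and timing, raw hours, survivors-only and worst rank each give 2.3-2.5%. In the 40% vs 25% case, worst rank significantly favours placebo in 5.4%, 11.6% and 32.9% of trials, because it counts the excess deaths as harm.

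The raw-hours figure depends on the death model. With death at a uniform 15-100% of the time the patient would have needed to wean, the 40% vs 25% results are 3.7%, 6.0% and 13.1%. With fatal cases dying at a uniform 3-48 h, counted as deaths on vasopressors if that precedes weaning, the result is 20.2%.

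**4. True 12 h effect** (midodrine hours x 42.9/54.9), equal 25% mortality. Raw hours and survivors-only disagree on significance in 16%, 17% and 24% of trials, or 15%, 15% and 19% with a 40 h median. With no effect, taking the better of the two gives a false benefit of 3.6%, 3.7% and 3.9%.

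**5. Where the death rule must reach.** Suppose the worst rank applied only to patients who die while the infusion is running. A patient whose vasopressors are stopped shortly before death would still be scored by short hours. At 40% vs 25% mortality, if 50%, 75% or 100% of the deaths otherwise before liberation follow such a stop, the false benefit is 1.1%, 5.0% and 14.9%. The last is about the same as raw hours.

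**The case against.** The strongest reply is that the error rates are mostly assumed. Time to death, the share of deaths before liberation and any imbalance between arms are not in the documents. The 25-30% has no time window, so all deaths preceding liberation is an upper bound. With a 40 h median to death the inflation is small. The hours use a published mean and SD that the plan itself considers less accurate than its repository data. Survivors-only scoring, which the arithmetic implies, stayed at 2.0-2.8% in no-effect runs; pushing it higher takes a pattern in which the deaths removed relate to duration differently by arm. All of this stands, and the percentages are illustrations.

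Second, 28-day and ICU mortality are reported, so an excess of deaths would be seen. That is true, but they would not show earlier deaths at equal mortality, and they do not alter the primary result.

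Third, worst rank is not the only remedy. Vasopressor-free days with a defined value for deaths, or a competing-risk analysis, could also serve. That is fair: what matters most is that one rule is fixed in advance.

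A reader might infer that Human Participants, item 1, proves a rival analysis set, since it says "Enrolling 115 patients would allow randomization of 50 patients to placebo and 50 patients to the midodrine dose". The documents do not support that. Items 3 and 4 of the same section give 149, as does 45 + 104 elsewhere. The 115 carries no allowance for mortality although its sentence cites 25%. It is a separate inconsistency and only weak evidence of another reading.

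**Conclusion.** The gap is real and should be closed before analysis. The complete-study primary outcome is undefined for patients who die before liberation, and its literal reading ranks an early death on vasopressors favourably, contrary to the stated aim. This conclusion needs no simulation.

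The size is conditional. Under the stated assumptions, raw hours give a false benefit of about 4% to 15% against 2.5% at 40% versus 25% mortality with a 27 h median to death, and about 3% to 6% with a 40 h median. The choice between the two readings changes significance in about 15-24% of trials with a true 12 h effect.

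Two stronger readings are tempting. One is that the plan as written inflates the type I error. It does not when mortality and death timing are equal, and nothing in the documents indicates that midodrine raises or hastens mortality. The other is that 25-30% of patients would be mis-scored. Only deaths before liberation are affected, and the documents do not say how many those are.

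**What to change.** In Statistical Considerations, item 4, state the following:

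- **Analysis set:** all patients randomised to placebo or the continuing midodrine arm (about 67 each), in their assigned arm.
- **Deaths:** within a fixed horizon such as 28 days, the worst rank goes to any patient who dies on IV vasopressors or within a pre-specified interval (for example 24 h) after their last stop, including a stop at withdrawal of care.
- **All others:** total hours on IV vasopressors to the horizon, including hours after re-initiation. Study Procedures, item 2, accepts that restarts may occur.
- **Test:** Mann-Whitney as planned, with survivors-only hours and mortality by arm as supportive results.

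Then re-run the repository bootstrap with this outcome. The extraction is described as "We then extracted their duration of vasopressors and the total norepinephrine equivalent doses at 24 hours"; death is not listed, so death status and timing may have to be added. Restate the power or the detectable effect without adding patients.

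**Cost:** wording and a re-run. The trial already collects vasopressor duration and mortality. The real price is that the primary outcome becomes a composite of death and weaning time, and power for 12 h may fall below the stated 80%. Illustratively, ranking deaths before liberation worst gives about 70%, 58% or 35% power if a quarter, half or all deaths precede liberation, against about 69% for survivors-only under the same assumptions. The effect detectable with 80% power is then about 13.5, 15.3 or 20.2 h, against about 13.5 h for survivors-only. Deaths caught by the interval after a stop add to the share ranked worst, so only the bootstrap can give the sponsor's own figure.
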